5.4.3.4.2. Analysis of Spirometry and DLCO

Spirometry:

The following outputs will be produced for PFTs, both for the Combined Analysis Period, using SAF, and for the Extension Analysis Period, using the EXTS:

- Summary of absolute values for PFT parameters (FEV₁, FVC, FEV₁/FVC ratio, %PRED FEV₁, %PRED FVC): descriptive statistics by visit;
- Summary of absolute change from baseline values for PFT parameters (FEV₁, FVC, FEV₁/FVC ratio, %PRED FEV₁, %PRED FVC): descriptive statistics by visit;
- Summary of percent change from baseline values for PFT parameters (FEV₁, FVC, FEV₁/FVC ratio, %PRED FEV₁, %PRED FVC): descriptive statistics by visit;
- Summary of absolute change from baseline values for PFT parameters (FEV1, FVC, FEV₁/FVC ratio, %PRED FEV₁, %PRED FVC): mean plot with core study treatment group color-coded (plot starting with zero change at baseline).
- Summary of percent change from baseline values for PFT parameters (FEV₁, FVC, FEV₁/FVC ratio, %PRED FEV₁, %PRED FVC): mean plot with core study treatment group color-coded (plot starting with zero change at baseline).

In addition, the following outputs will be produced both for the Combined Analysis Period, using the SAF and only for subjects who received ponesimod 20 mg in the core study, and for the Extension Analysis Period, using the EXTS:

• Incidence of treatment-emergent spirometry outliers [as defined in Section 5.4.3.4.1]: frequency counts, percentages, where percentages are based on the number of subjects with at least one treatment-emergent result available for the corresponding parameter.

Unscheduled visits are not presented in summary tables by visit. Unscheduled assessments that meet the pre-defined high/low criteria will be flagged and may be included in the corresponding incidence tables.

All notable abnormality in spirometry results (best effort results from core study and all results from extension study) will be listed by study treatment group and visit.

In addition, to understand the change in PFT parameters (FEV1, FVC, FEV1/FVC ratio, %PRED FEV1, %PRED FVC) after EOT, the following analyses will be done for subjects who continue any DMT (see section 6.5.1.4 for DMT list) after EOT date versus subjects who have no DMT after EOT date (irrespective of the original treatment group):

- Absolute values of PFT parameters over the following visits: Core baseline, Extension Baseline, Extension EOT, Extension EOS and the change from Core baseline using EXTS.
- A line graph to present the percent change from core baseline in PFT parameters over the following visits: Core baseline, Extension Baseline, Extension EOT, Extension EOS.

Note that the group labels in this analysis are "Any DMT" and "No DMT", irrespective of the treatment group. Only subjects who have EOS visit and the EOS visit is at least 5 days after the EOT date are included in this analysis (refer to section 5.5.6 for more details).

Spirometry (Pulmonary Function Tests) - DL_{CO}

The following summary displays are provided, by study treatment group, for the Combined Analysis Period (the summaries marked with § will include only the subjects who were initially treated with ponesimod 20 mg in the core study) on the DLco sub-study safety analysis set, and for the Extension Analysis Period on the DLco sub-study extension analysis set:

- Treatment-emergent Hemoglobin corrected DLco, percent predicted DLco and DLco including absolute and percent change from core baseline, as described in Section 5.4.3.4.1, are presented, by parameter and visit. Except for 'Baseline', only treatment-emergent results from nominal scheduled visits are included; premature EOT visit is mapped to a scheduled visit. These are summarized descriptively and mean absolute and percentage changes from baseline are also presented graphically with their standard error over time (plots starting with zero change at baseline).
- Number and percentage of subjects with any occasion of treatment-emergent low Hemoglobin corrected DLco, Percent predicted DLco, and DLco values as defined in Section v are presented. Percentages are based on the number of subjects with at least one treatment-emergent result available for the corresponding parameter.§

All notable abnormality DL_{CO} results (derived mean values per assessment) are listed by study treatment group and visit.

5.4.3.5. Dermatological Examination

Collected in the Dermatological Examination eCRF. No definitions and derivations necessary. Any resulting findings are recorded as adverse event (or medical history). No additional statistical outputs are needed in this field.

5.4.3.6. Optical coherence tomography

Collected in the Optical coherence tomography (OCT) eCRF. No definitions and derivations necessary. Any resulting findings are recorded as adverse event (or medical history or relapse). No additional statistical outputs are needed in this field.

5.4.3.7. Ophthalmological Examination

Data will be taken from both Ophthalmological Examination eCRFs. No definitions and derivations necessary. Any resulting findings are recorded as adverse event (or medical history or relapse). No additional statistical outputs are needed in this field.

5.4.3.8. Physical examination

No definitions and derivations necessary. Any resulting findings are recorded as adverse event (or medical history or relapse). No additional statistical outputs are needed in this field.

5.4.3.9. Electronic self-rated version of the Columbia-Suicide Severity Rating Scale (eC-SSRS)

5.4.3.9.1. Definition of eC-SSRS variables

The electronic self-rated version of the Columbia-Suicide Severity Rating Scale (eC SSRS©) is an assessment instrument that evaluates suicidal ideation and behavior. During an initial assessment it assesses lifetime as well as the recent history suicidality (scheduled at Core study

Visit 2-Baseline), and then prospectively monitors ideations and behaviors at subsequent follow up assessments since the last call throughout Core and Extension study.

The eC-SSRS outcome categories are provided below. The categories are ordered by increasing seriousness. Each category has a binary response (yes/no) and are numbered and ordered below for convenience

Table 8: eC-SSRS outcome categories

	Question category	Label in QSTEST in QS dataset				
Suicidal Ideation (1-5)	Category 1: Wish to be dead	"CSS01-Wish to be Dead" and "CSS02-Wish to be Dead"				
	Category 2: Non-specific active suicidal thoughts	"CSS01-Non-Specific Suicidal Thought" and "CSS02-Non-Specific Suicidal Thought"				
	Category 3: Active suicidal ideation with any methods (not plan) without intent to act	"CSS01-Suicidal Ideation-No Intent" and "CSS02-Suicidal Ideation-No Intent"				
	Category 4: Active suicidal ideation with some intent to act, without specific plan	"CSS01-Ideation With Intent, No Plan" and "CSS02-Ideation With Intent, No Plan"				
	Category 5: Active suicidal ideation with specific plan and intent	"CSS01-Ideation With Plan/Intent" and "CSS02-Ideation With Plan/Intent"				
Suicidal Behavior (6-10)	Category 6: Preparatory acts or behavior	"CSS01-Preparatory Acts/Behavior" and "CSS02-Preparatory Acts/Behavior"				
	Category 7: Aborted attempt	"CSS01-Aborted Attempt" and "CSS02-Aborted Attempt"				
	Category 8: Interrupted attempt	"CSS01-Interrupted Attempt" and "CSS02-Interrupted Attempt"				
	Category 9: Non-fatal suicide attempt	"CSS01-Most Lethal Attempt Damage", "CSS01-Most Recent Attempt Damage", "CSS01-Most Lethal Attempt Potential", "CSS01-Most Recent Attempt Potential", "CSS02-Most Lethal Attempt Damage" "CSS02-Most Lethal Attempt Potential"				
(Category 10: Completed suicide					

CONFIDENTIAL – FOIA Exemptions Apply in U.S. Status: Approved, Date: 04 March 2024

Furthermore, **self-injurious behavior without suicidal intent** is also an eC-SSRS outcome (although not suicide-related) and has a binary response (yes/no), this will be assigned as score 11 and to be summarized for subjects with these events.

The initial assessment has a lifetime and a recent history assessment. The recent history covers the last 1 month for suicidal ideation, and the last 3 months for suicidal behavior. Recent history questionnaire questions are only assessed for outcome categories with corresponding lifetime outcome question answered as yes. If the lifetime assessment for an outcome category is 'No', also the corresponding recent history outcome is considered 'No' for analysis. The "lifetime and a recent history assessment" is performed twice during the course of the study, respectively at core study baseline and at extension visit 7 – week 48.

Scoring: Scores are created at each assessment as follows:

- **Suicidal Ideation Score**: The maximum suicidal ideation category (1–5 on the eC-SSRS) present at the assessment. Assign a score of 0 if no ideation is present.
- **Suicidal Behavior Score:** The maximum suicidal behavior category (6–10 on the eC-SSRS) present at the assessment. Assign a score of 0 if no behavior is present.

For each assessment timepoint, a subject with multiple reported outcomes for suicidal ideation and suicidal behavior will be summarized under the worst reported outcome (i.e., max[1-5] and max[6-10], respectively).

Throughout all post-baseline assessments, a subject can have multiple suicidal ideation or suicidal behaviors, the worst reported outcome will be considered as the post-baseline outcome.

The following definitions will be used:

- Suicidal ideation: A "yes" answer to any one of the five suicidal ideation questions (Categories 1-5) on the eC-SSRS. Taken from the 'Reported most severe ideation level'.
- **Suicidal behavior**: A "yes" answer to any one of the five suicidal behavior questions (Categories 6-10) on the eC-SSRS.
- Suicidal ideation or suicidal behavior
- Serious suicidal ideation (score \geq 4) or suicidal behavior

The definitions above will be defined at any time in the period from study treatment start up to Extension EOT + 15 days*, for pre-treatment lifetime, and for pre-treatment recent history.

Suicidal Ideation and Suicidal Behavior score categories: Shifts from baseline (worst outcome from pre-treatment recent history) to the worst outcome up to Extension EOT + 15 days (inclusive) will be derived using the following categories: No ideation (score 0), non-serious suicidal ideation (score 1-3), serious suicidal ideation (score 4-5), suicidal behavior (score 5-10).

*Only post-baseline assessments after study treatment start date from a 'since last call' questionnaires and the "Recently" questionnaire assessed at B303 extension week 48 (visit 7) are considered for the analysis.

Baseline is defined as last available recent history result (maximum score) up to study treatment start date at core study, i.e., pre-treatment recent history result at core baseline. This is taken from the answers to the "Recently" category questionnaires at core study baseline. If the lifetime assessment at core study baseline for an outcome category is 'No', also the corresponding recent

history outcome is considered 'No' for analysis. The core study baseline has already been derived and captured in B301 ADaM dataset and can be used directly.

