5.4.2.2.8. Deaths

Death information (date of death and primary cause) is taken from the Death eCRF.

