5.4.3.9.2. Analysis of Columbia Suicide ideation or behavior

Number (%) of subjects with suicidal ideation (overall and by category), suicidal behavior (overall and by category), suicidal ideation score ≥ 4 or suicidal behavior and/or self-injurious behavior without suicidal intent will be tabulated by treatment group at Core baseline visit and at Extension week 48. The "Lifetime" and "Recently" results will be summarized separately. In addition, the worst outcome of post-core-baseline assessment up to Extension EOT + 15 days (including the assessment at Extesion week 48) will be presented. Analyses will be based on subjects in the SAF and EXTS who have at least one eC-SSRS measurement during Combined analysis period available.

For subjects who have in addition a core baseline eC-SSRS assessment available shifts from core baseline (maximum score from pre-treatment recent history) to the worst reported outcome (the maximum score) up to Extension EOT + 15 days will be tabulated by treatment group to demonstrate any changes in Suicidal Ideation and Suicidal Behavior score categories (i.e. No ideation, non-serious suicidal ideation, serious suicidal ideation).

A listing will be generated for subjects who have positive value of any Suicidal Ideation, Suicidal Behavior or Self-Injurious Behavior without Suicidal Intent of that visits. To be specific, if a subject had outcome "Y" in the Suicidal ideation category "1-Wish to be Dead" at Extension visit 11, all suicidality scores of that visit will be listed. On the contrary, if all outcomes of suicidality score are negative then this visit won't be listed.

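### Completed suicide is category 10 of the eC-SSRS behavior score, but only self-rated questionnaire answers can set the score, so that row is zero by construction

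*SAP*

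**What the plan says.** Section 5.4.3.9.1 describes the instrument as "The electronic self-rated version of the Columbia-Suicide Severity Rating Scale". Table 8 gives ten ordered outcome categories, each with a yes/no response. The last, under suicidal behavior, is "Category 10: Completed suicide". The Suicidal Behavior Score is the highest of categories 6 to 10 present at an assessment, or 0 if there is none. Suicidal behavior is a yes "answer to any one of the five suicidal behavior questions (Categories 6-10) on the eC-SSRS".

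Across post-baseline assessments, "the worst reported outcome will be considered as the post-baseline outcome". The data allowed into that derivation are restricted: "Only post-baseline assessments after study treatment start date from a 'since last call' questionnaires", together with the recent-history questionnaire at extension Week 48.

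Section 5.4.3.9.2 tabulates behavior overall and by category. It also tabulates shifts from core baseline "to the worst reported outcome (the maximum score) up to Extension EOT + 15 days". The population is subjects in the SAF and EXTS with at least one eC-SSRS measurement in the Combined Analysis Period, shown by treatment group.

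Deaths follow a separate path. Section 5.4.2.2.8 says: "Death information (date of death and primary cause) is taken from the Death eCRF". Section 5.4.2.3.2 tabulates deaths in the extension study by core treatment group with primary cause, and adds a listing of all deaths.

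**The concern.** The plan puts completed suicide at the top of a scale and then fills the scale only from answers given by the subject. Nobody can report their own completed suicide on a questionnaire. A zero in the category 10 row would therefore say nothing about what happened in the trial, yet in a table by category it reads like an observed zero. In the worst-outcome and shift tables, a subject who died by suicide would sit in a milder class, possibly the mildest. At stake is the meaning of the suicidality outputs and their agreement with the death data in the same report.

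**Working it through.** The SAP gives no figure to reproduce. The check follows its rules for a subject who dies by suicide while on study treatment.

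1. *Source of the score.* Category 10 needs a yes on the eC-SSRS (5.4.3.9.1). After baseline, only the since-last-call questionnaires and the Week 48 recent-history questionnaire count. No questionnaire follows the death, so category 10 cannot be set.
2. *Other routes.* Cause of death comes from the Death eCRF (5.4.2.2.8) and fatal outcome from the adverse event record (5.4.2.2.7). Neither section, nor 5.4.3.9, passes this information to the score.
3. *What the tables then show.* The post-baseline outcome is the maximum over post-baseline questionnaires. Illustrative subjects, each dying by suicide before the next questionnaire:

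| Post-baseline scores before death | Outcome under the SAP | Effect |
|---|---|---|
| 4, then 0 | max(4, 0) = 4, serious ideation | Too mild |
| 0, 0 | max(0, 0) = 0, no ideation | Mildest class instead of worst |
| 9, then 0 | max(9, 0) = 9, suicidal behavior | Shift class right, category row wrong |
| none | no post-baseline outcome | Absent from the worst-outcome table |

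4. *Spacing of questionnaires.* The Appendix 12 schedule places the extension eC-SSRS at Weeks 48, 96, 144, 192 and EOT. Consecutive scheduled assessments are 96 − 48 = 48 weeks apart, so the last questionnaire can precede a death by most of a year.
5. *Coverage elsewhere.*

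| Output | Period | Subjects |
|---|---|---|
| eC-SSRS worst outcome and shift (5.4.3.9.2) | Combined | Both core treatment groups |
| Deaths table with cause (5.4.2.3.2) | Extension only | Both groups |
| Combined-period AE and SAE tables (5.4.2.3.1, 5.4.2.3.3) | Combined | Started on ponesimod only |
| Fatal SAE table (5.4.2.3.3) | As for AEs | Only if more than 5 fatal events |
| Listing of all deaths; listing of fatal SAEs | All recorded | Not a summary table |

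Consider a teriflunomide subject who died by suicide during the core study. With at least one post-baseline questionnaire, that subject is in the eC-SSRS tables at an earlier score. The deaths table and the combined-period AE tables of this SAP exclude the death, which leaves only the listings.

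**The case against.** The strongest reply is that the eC-SSRS tables report questionnaire answers, deaths are reported elsewhere, and a zero in a questionnaire table does not claim that nobody died. On this view category 10 is an editorial leftover from the published scale. All analyses are exploratory (section 2), and the eC-SSRS is not among the safety endpoints in Table 2. Much of this stands: it limits the point to the suicidality outputs and makes removal of category 10 an acceptable remedy. It does not remove the point, because the SAP includes category 10 in the score range and the behavior definition and then tabulates by category.

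Some stronger readings are tempting but unsupported:

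- *The subject keeps the last questionnaire score.* The SAP takes the maximum, so scores of 4 and then 0 give 4.
- *Every suicide moves from the worst class to the best.* That happens only if all post-baseline answers were negative. The shift classes in 5.4.3.9.1 pool all suicidal behavior, so a subject with an earlier reported attempt is already in the top class.
- *The suicide is concealed.* It would appear in the death listing and, for the extension, in the deaths table by cause.
- *The empty Table 8 cell for category 10 proves the defect.* The table may have lost text in extraction. The argument rests on the definition and the data restriction instead.

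**Conclusion.** The defect holds within the eC-SSRS outputs. Under the stated rules the category 10 count is 0 in any dataset, and a subject who dies by suicide is shown at the worst earlier self-report. The error per subject runs from none in the shift table (earlier behavior reported) to the full width of the scale (all answers negative). Other outputs cover the death only in part, because the period and treatment groups differ.

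No probability of a suicide is given: it would need a suicide rate and person-years that the SAP does not state, and the defect does not depend on it. The conclusion assumes that no programming specification outside the SAP already links death records to the score. It has no bearing on efficacy or on other safety tables.

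**What to change.** Choose one of two edits to sections 5.4.3.9.1 and 5.4.3.9.2.

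(a) *Derive category 10.* Take it from the Death eCRF primary cause, or from a fatal adverse event of completed suicide. The window runs from study treatment start to extension EOT + 15 days, or core EOT + 15 days for subjects who did not enter the extension. Set the Suicidal Behavior Score to 10 in the worst-outcome and shift tables for subjects already in the section 5.4.3.9.2 population. Use the four shift classes of 5.4.3.9.1, because the parenthesis in 5.4.3.9.2 names only three and omits suicidal behavior. Report a suicide in a subject without an eC-SSRS measurement in a footnote. Do not add that subject to the denominator: admitting unmeasured subjects only when they have the event turns x/n into (x + 1)/(n + 1), which is larger whenever x < n, and it departs from the stated population.

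(b) *Remove category 10.* Restrict the questionnaire-based definition and tables to categories 6 to 9, and footnote that completed suicides are reported under deaths.

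Option (a) costs a few sentences and a small merge of death and adverse event records into the eC-SSRS analysis dataset. Option (b) costs wording and a table footnote. Both use data already collected.

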MRI and C-SSRS: For MRI and C-SSRS measurements visit windowing of premature EOT visits is conducted using \pm 3 months around the target day (Week 48: Day 246 to Day 428; Week 96: Day 582 to Day 764; Week 144: Day 918 to Day 1100; Week 192: Day 1254 to Day 1436; Week 240: \geq Day 1590 for subjects who are not impacted by extended study duration, or Day 1590 to 1772 for Ukraine subjects with extended study duration; Week 288: \geq Day 1926 (this applies for Ukraine subjects with extended study duration due to regional crisis) Note: as planned pregnancy visits are considered scheduled MRIs for analysis, they are also re-mapped using the same rules.

CONFIDENTIAL – FOIA Exemptions Apply in U.S.

^{*} These analysis windows applied for Laboratory (LB) assessments only, as described

^{**} This applied for subjects not impacted by regional crisis

^{***} This applied for Ukraine subjects with extended treatment period and additional visits

MSFC and SDMT: For premature EOT visits which occurred before day 245, the remapping rules follow the same in Table 7. For premature EOT visits and the EOT visits from patients who switched to commercial ponesimod, the remapping of EOT visits follows the same rule as in MRI and C-SSRS.

SF-36: For SF-36 questionnaires collected via an electronic device visit windowing is applied as a general process. To ensure a more precise visit labels, questionnaires based on dates will be assigned to the visits as following. If multiple questionnaires are available, the one closest to target is selected. The visit windowing will also be applied to premature EOT assessments.

```
Week 24 -- Target: Day 169; Range: Day 1 to Day 252;
Week 48 -- Target: Day 337, Range: Day 253 to Day 504;
Week 96 -- Target: Day 673, Range: Day 505 to Day 840;
Week 144 -- Target: Day 1009, Range: Day 841 to Day 1176;
Week 192 -- Target: Day 1345, Range: Day 1177 to Day 1512;
Week 240 -- Target: Day 1681, Range: ≥ Day 1513 for subjects who are not impacted by extended study duration, or Day 1513 to 1848 for Ukraine subjects with extended study duration;
```

Week 288 -- Target: Day 2017, Range: ≥ Day 1849 (this applies for Ukraine subjects with extended study duration due to regional crisis).

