6.12. Appendix 12 Study visit and assessment schedule

Table 12 and Table 13 show a schematic representation of the assessments during the extension study

Table 12: Visit and assessment schedule

Periods	Name	AC-058B	301 (core study)	AC-058B303 (extension study) TREATMENT PERIOD									
	Duration		NA	Treatme	Treatment may continue until 240 weeks or until ponesimod is commercially available (whichever occurs first)								
	Number		NA	1	2	3	4	5	6, 8-10, 12-14, 16- 18, 20-22	7, 11, 15, 19	23		
Visits	Name	FU1 Core Study	Abbreviated FU2 Core Study (1)	Enrollment	W2	W4	W12	W24	W36, W60, W72, W84, W108, W120, W132, W156, W168, W180, W204, W216, W228	W48, W96, W144, W192	ЕОТ		
									Every 12 w	veeks	W240 or		
	Time	NA	NA	Day 1(2)	Day 15	Week 4	Week 12	Week 24		Every 48 weeks	earlier (14)		
	Visit window	NA	NA	NA	-1 to +3 days	±7 days	±7 days	±14 days	±14 days	±14 days	14 days		
Informed c				X									
Inclusion/e	xclusion criteria*			X									
Demograph				X									
Medical Hi	story*			X									
EDSS/FS*				X			X	X	X	X	X		
Relapse*		X	X	\leftarrow			Χ (3)			\longrightarrow		
SDMT*				`			X	X		X	X		
MSFC*										X	X		
SF-36**								X		X	X		
eC-SSRS*	*									X	X		
MRI**(15)										X	X		
Concomita	nt medications*	X	X	X	X	X	X	X	X	X	X		
	camination*			X				X		X	X		
Dermatolog	gical examination* (4)									X	X		
Body weig										X	X		
Body temp	erature*	X		X	X	X	X	X	X	X	X		
Systolic/dia	astolic blood pressure*(5)	X		X(5)	X	X	X	X	X	X	X		
12 Lead EC		X		X						X	X		
Pulse rate*	``				X	X	X	X	X				
Ophthalmo	logical examination / OCT						X	X		X	X		
Pulmonary	function tests* (8)	X				X				X	X		
	y/Chemistry**	X			Х	\leftarrow	(9)	\rightarrow	X	X	X		
Urinalysis*		X			1	`		X	X	Х	X		
Pregnancy	test*/** (10)	X		X	1	X	X	X	X	X serum	X serum		
Elimination	n procedure compliance	X	X	-	İ	·-							
	ide plasma concentration			X (11)									
Additional serology*	serum sample for viral			X									
Study treat	ment dispensing &			X	X	х	х	X	X	X	Х		
AEs* / SAl		X	X	X	X	X	X	X	X	X	X		

- * Data collected in the eCRF
- ** Electronically transferred to the sponsor

Day 1 (date of treatment start) is to be used as the reference date for the purpose of calculating the subsequent visit dates (and time windows).

- 1) This visit will only take place if the compliance with the teriflunomide elimination procedure in the core study was not sufficient and has to be re-assessed prior to the study drug administration on Day 1.

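### The eC-SSRS worst-outcome and shift tables claim coverage from treatment start to extension EOT + 15 days, but the sources admitted around extension Week 48 leave most of the preceding 48 weeks uncovered

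*SAP*

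**What the plan says.** SAP 5.4.3.9.1 defines a post-baseline outcome over the whole follow-up: "Throughout all post-baseline assessments, a subject can have multiple suicidal ideation or suicidal behaviors, the worst reported outcome will be considered as the post-baseline outcome". It applies the ideation and behavior definitions to the full interval from study treatment start to 15 days after extension EOT. Section 5.4.3.9.2 tabulates "the worst outcome of post-core-baseline assessment up to Extension EOT + 15 days" and a shift table from core baseline to that worst outcome.

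A footnote in 5.4.3.9.1 limits the sources. The first is "Only post-baseline assessments after study treatment start date from a 'since last call' questionnaires". The second is the 'Recently' "questionnaire assessed at B303 extension week 48 (visit 7) are considered for the analysis".

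Three further statements matter:

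- The lifetime and recent-history version "is performed twice during the course of the study, respectively at core study baseline and at extension visit 7 – week 48" (5.4.3.9.1).
- On the look-back: "The recent history covers the last 1 month for suicidal ideation, and the last 3 months for suicidal behavior" (5.4.3.9.1).
- In Table 12 (6.12) the eC-SSRS is marked only in the every-48-weeks column ("W48, W96, W144, W192") and at EOT. Table 13 has no eC-SSRS row.

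The Week 48 'Lifetime' answers are summarized separately, as at core baseline (5.4.3.9.2). They are not among the sources of the worst outcome.

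**The concern.** The last core assessment and extension Week 48 are separated by roughly a year. If the Week 48 visit enters the worst outcome only through a 1- or 3-month look-back, earlier ideation or behavior that has resolved by then is lost to that outcome. The Week 96 questionnaire does not recover it, because it asks only about the time since the Week 48 call.

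Take a subject who switched from teriflunomide, was lifetime-negative at core baseline, and had ideation with intent at extension Week 10 that then resolved. At Week 48 the subject answers Yes under 'Lifetime' and No under 'Recently'. With no other positive assessment, the worst-outcome and shift tables show no post-baseline ideation.

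The error runs in one direction, towards too few events. For former teriflunomide subjects the uncovered time is most of their first year on ponesimod, and 5.1.5.2 names that switch as something the safety analysis is meant to examine. Nothing in the section tells the reader of the gap.

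**Working it through.** The SAP gives no coverage figure to reproduce, so this is arithmetic on the look-back.

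**Inputs**

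- Week 48 target: Day 337, so 337 − 1 = 336 days from Extension Day 1. Table 7 in 5.1.10 gives this nominal day, the SF-36 list in the same section agrees ("Week 48 -- Target: Day 337, Range: Day 253 to Day 504"), and the C-SSRS window there, Day 246 to 428, is centered on it: (246 + 428)/2 = 337.
- Look-back: 1 month (ideation) and 3 months (behavior), from 5.4.3.9.1. I take a month as 30.4375 days.
- Full combined period: 108 core weeks + 240 extension weeks = 348 weeks = 2436 days (1.2 and 1.2.3).

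**Formula:** uncovered days = 336 − look-back; share = uncovered days / 336.

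| | Look-back (days) | Uncovered days | Weeks | Share of 336 days | Share of 2436 days |
|---|---|---|---|---|---|
| Ideation | 30.4 | 336 − 30.4 = 305.6, about 306 | 43.7 | 91% | 306/2436 = 12.6% |
| Behavior | 91.3 | 336 − 91.3 = 244.7, about 245 | 35.0 | 73% | 245/2436 = 10.1% |

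**Sensitivity**

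- Months of 28 to 31 days and the ±14-day visit window of Table 12 give 90.5% to 92% for ideation and 72% to 75% for behavior.
- Counting from core EOT, with an assumed gap of 15 to 45 days to Extension Day 1 and the last core eC-SSRS assumed to be at core EOT, the shares are 91% to 92% and 74% to 76%.

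**Which questionnaire is given at Week 48.** Section 5.4.3.9.1 names the lifetime/recent version for that visit, and the footnote adds 'Recently' at Week 48 as a special source. That addition would serve little purpose if a 'since last call' questionnaire covering the same time had also been given. Replacement is therefore a strong inference, but the SAP does not state it.

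**The case against.** Several stronger readings are tempting, and the SAP does not support them.

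- A reader might infer that the whole worst outcome rests on the Week 48 'Recently' answers. It does not: 'since last call' questionnaires in the core study and at the other extension visits also count.
- A reader might infer that gap events are counted nowhere. Section 5.4.3.9.2 tabulates Week 48 'Lifetime' answers by treatment group and lists all scores from any visit with a positive answer, and an event may be reported as an AE. The claim is limited to the two derived tables. That said, the 'Lifetime' table mixes gap events with pre-treatment history, so it cannot show them as post-baseline.
- A reader might set the gap against the 240 extension weeks (1680 days), giving 306/1680 = 18% and 245/1680 = 15%, or multiply it by all 877 enrolled subjects. The affected tables start at core baseline, so the longer denominator applies. Not everyone reached Week 48, subjects with an earlier EOT may have a 'since last call' assessment covering their time, and SAF subjects who never entered the extension have no gap.

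It can also be argued that the cause lies in data collection, that leaving undated 'Lifetime' answers out of a treatment-emergent outcome is reasonable, that the eC-SSRS is not among the Table 2 endpoints, and that all analyses are exploratory (section 2). These points limit the priority. They do not reconcile the coverage that 5.4.3.9.1 claims with the sources it admits.

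**Conclusion.** The point holds for the worst post-baseline outcome and the shift table. For subjects whose first extension assessment is Week 48, about 91% (ideation) and 73% (behavior) of the preceding 336 days are not covered, or about 12.6% and 10.1% of a full 348-week combined period. The share of the combined period is larger for subjects who stop soon after Week 48 and smaller for Ukraine subjects treated beyond Week 240.

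This rests on two assumptions: that 'since last call' was not also given at Week 48, and that no unscheduled eC-SSRS fell in the gap. The number of affected events cannot be judged from the SAP. The analyses are descriptive, but a rule that turns a resolved event into 'none' in a suicidality table merits a cheap correction.

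**What to change.** In 5.4.3.9.1:

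1. State which questionnaire version was given at extension Week 48. If 'since last call' was also given, use it in the worst outcome; steps 2 to 4 are then unnecessary.
2. Otherwise, count as a post-baseline event any category answered 'Lifetime' Yes at Week 48 that was 'Lifetime' No at core baseline, and include it in the worst-outcome and shift tables.
3. Show on a separate row those not already reported by a core 'since last call' questionnaire (or by Week 48 'Recently'), labeled as occurring between core baseline and extension Week 48, not otherwise reported.
4. Footnote that, for subjects already lifetime-positive in a category at core baseline, extension Weeks 0 to about 44 (ideation) or 35 (behavior) remain uncovered.

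The cost is SAP wording and one derivation. No new data are needed: 'Recently' is asked only where 'Lifetime' is Yes, so every completed Week 48 assessment holds the 'Lifetime' answers. The downside is some misclassification. A few new positives may be older events not reported at core baseline, or core-period events, so the separate row does not isolate the time after the switch and should be read that way.
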